## 7.3 Follow-up of adverse events

All adverse events will be followed until they have abated, or until a stable situation has been reached. Depending on the event, follow up may require additional tests or medical procedures as indicated, and/or referral to the general physician or a medical specialist.

#### 8. STATISTICAL ANALYSIS

#### 8.1 Descriptive statistics

Descriptive statistics will be provided for the OQ scores per session (mean scores and standard deviations), the characteristics of the patient and therapist samples (proportions of males/female, mean, range and standard deviation of age, mean years of experience, proportion of patients with previous treatment) and patient diagnosis (proportion of patients with comorbidity, frequency of diagnostic categories).

#### 8.2 Multivariate analysis

The data will be analysed using a three-level random intercept, random slope multilevel model, with repeated measures at level 1, patients within therapists at level 2 and therapists at level three. Randomisation takes place at the patient level (level 2). The OQ-45 total score is the dependent variable. The treatment conditions will be recoded into two dummy variables. Initial severity on the OQ-45 at start of treatment will be included in the model as a covariate for both the intercept and slope prediction.

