## 4.4 Sample size calculation

Performing an a priori power analyses for multilevel analysis is complicated, because one has to have a good estimate of the variance components in advance and these are usually unknown, especially for three level models and three research conditions (de Jong, Moerbeek & Van der Leeden, 2009). An a priori power analysis was performed for two research conditions, based on the variance components of previously collected data, which resulted in approximately 4 patients per therapist, and 50 therapists participating for a power of 0.80, which is generally considered to be sufficient. However, this analysis was performed with an intended moderate effect (Cohen's d = 0.50), whereas feedback metaanalysis shows a small effect (Cohen's d=0.30). Also, in the current study we have three research conditions, which is considerably more complicated to model. The difference between the two feedback conditions is most likely smaller than d=0.30. Another thing that needs to be considered is that the effect only applies to the "not on track" group. As this group consists of approximately 25% of the total patient group and we cannot identify this group beforehand, the number of patients that need to be included in the study needs to be four times as large as the results from the a priori power analysis.

A traditional a priori power analysis was performed in G\*Power 3.0.10 for F tests with repeated measures, three research groups, three repeated measures, a power coefficient of 0.80, an  $\alpha$  of 0.05, and a correlation of 0.70 between the repeated measures. This resulted in a needed sample size of 90 not on track patients. The total sample size needed would then be 360 patients. This analysis does not take into account that patients are nested within therapists and therapists will explain part of the variance. We know from a previous study that the intraclass correlation was 0.18 at the therapist level. A rule of thumb to correct for the variance at the therapist level is to use the formula for the design effect:  $1 + (k-1)^{*icc}$ , with k being the number of patient per therapist, we would get a design effect of: 1 + 3 \* 0.18 = 1,54. This means that  $1.54^{*}360 = 554$  patients need to be included in the study. As we expect that some of the data will not be valid, the number of 600 patients was chosen as targeted *N*.

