#### **Procedure**

All patients that asked to participate in this study will be interviewed with the MINI Plus as part of the standard intake procedure. After patients agree to participate the research assistant will adminster the SCID-II PQ. As from start of treatment, participants will be asked to complete the OQ-45 before each session, for a maximum of 15 sessions and/or one year. In addition, the OQ-45 will be administered 3 and 6 months after treatment (or study) termination. In the ETR feedback condition, patients will fill out the ASC when they are going off track. In the ROM feedback condition and control condition, patients will fill out the ASC when they would have signalled, but the therapist will receive no feedback on how the patient responded.

Therapists will be asked to complete the EOQ on each of their patients at sessions 1, 5, 10 and 15 or the end of treatment, if this is within 15 sessions. The UOF will be administrated after sessions 5, 10 and 15 or the end of treatment. To measure therapists' attitude towards getting feedback, the CFITUS will be administered before the start of the study, after six months, after one year and after a year and a halve. At the first administration, before the start of the study, the EFPS and GSE will be filled out by the therapists as well.

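### The power of 0.80 in section 4.4 belongs to a comparison among not-on-track patients, but the model in section 8.2 tests condition in all patients, for whom no power is stated

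*Protocol*

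**What the plan says.** Section 4.4 takes the feedback effect to be confined to patients who are not on track. It gives the reason for enlarging the trial: "As this group consists of approximately 25% of the total patient group and we cannot identify this group beforehand". The calculation is a repeated-measures F test with "three research groups, three repeated measures, a power coefficient of 0.80" and "a correlation of 0.70 between the repeated measures". It yields 90 not-on-track patients, which becomes 360 in total, 554 after a design effect of 1.54, and a target of 600. No effect size is given for this run. The section mentions d = 0.50 for an earlier two-condition analysis, notes "whereas feedback metaanalysis shows a small effect" (d = 0.30), and adds "The difference between the two feedback conditions is most likely smaller than d=0.30".

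Section 8.2 names the analysis: "The data will be analysed using a three-level random intercept, random slope multilevel model". The outcome is the OQ-45 total score, condition enters as two dummies, and initial severity is a covariate for intercept and slope. Not-on-track status does not appear. The primary objectives in section 2 are not limited to that group, and the Summary says data from every patient can be used.

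The Procedure part of section 6.3 shows that signalling is tracked in the ROM and control arms too: "patients will fill out the ASC when they would have signalled, but the therapist will receive no feedback".

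**The concern.** The protocol names a powered population in one section and a primary model in another, and they do not match. Read literally, 8.2 averages the patients in whom 4.4 expects an effect with the three quarters in whom it expects none. A reader who takes 0.80 from 4.4 and the model from 8.2 would credit the planned test with power that was calculated for a different one.

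This also affects conduct. Sections 4.4 and 8.3 plan a power analysis after six months that may prolong inclusion, and its result depends on which test is being powered.

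**Working it through.** **Inputs.** From section 4.4: alpha 0.05 (taken as two-sided for pairwise tests), power 0.80, 3 groups, m = 3 measures, correlation 0.70, not-on-track share 25%, therapist ICC 0.18, N = 90 / 360 / 554 / 600, and d = 0.30 as the cited small effect. From section 1: d = 0.21 overall. Assumed: equal allocation, so 200 per arm, or 600/1.54/3 = 130 per arm after the design effect.

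**Step 1: reproduce the plan's figure.** For the between-groups repeated-measures F test, lambda = N·m·f²/(1 + (m−1)·rho), with 2 and N−3 degrees of freedom. With f = 0.30, lambda = 90·3·0.09/2.4 = 10.125 and power is 0.806, so N = 90 reproduces. Solving for exactly 0.80 gives f = 0.298. If the test was the group-by-time interaction, lambda = N·m·f²/(1−rho), with 4 and 2(N−3) degrees of freedom, and f = 0.117. Taking d = 0.30 as the two-group f = 0.15 in the between-groups test would need 348 patients, not 90. The remaining steps are right: 90/0.25 = 360; 1 + 3·0.18 = 1.54; 1.54·360 = 554.4.

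**Step 2: dilute the effect behind N = 90.** The all-patient effect is 0.25·effect + 0.75·0, a quarter of the effect. Lambda is proportional to N·f², so four times the patients at a quarter of the effect multiplies it by 4/16 = 1/4.

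| All-patient N | Between-groups test | Interaction test |
|---|---|---|
| 360 | 0.27 | 0.25 |
| 390 (= 600/1.54) | 0.29 | 0.27 |
| 600, clustering ignored | 0.43 | 0.40 |

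**Step 3: pairwise comparisons.** With d = 0.30 in the not-on-track group, the all-patient d is 0.25·0.30 = 0.075. SE = sqrt(v·(1/n1 + 1/n2)) and power = Phi(d/SE − 1.96) + Phi(−d/SE − 1.96). Four values of v cover a single measure (1), the mean of three measures ((1 + 2·0.7)/3 = 0.80), baseline adjustment (1 − 0.7² = 0.51), and baseline adjustment with therapist variance also removed (0.51·0.82 = 0.418).

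| Comparison | d | n | v = 1 | 0.80 | 0.51 | 0.418 |
|---|---|---|---|---|---|---|
| All patients, one feedback arm v control | 0.075 | 200 v 200 | 0.117 | 0.134 | 0.183 | 0.213 |
| Same, after design effect | 0.075 | 130 v 130 | 0.093 | 0.104 | 0.135 | 0.155 |
| All patients, feedback arms pooled v control | 0.075 | 400 v 200 | 0.139 | 0.162 | 0.228 | 0.268 |
| All patients, milder dilution | 0.21 | 200 v 200 | 0.556 | 0.651 | 0.837 | 0.901 |
| Same, after design effect | 0.21 | 130 v 130 | 0.395 | 0.473 | 0.659 | 0.745 |
| Not on track, one feedback arm v control | 0.30 | 50 v 50 | 0.323 | 0.389 | 0.556 | 0.640 |
| Not on track, feedback arms pooled v control | 0.30 | 100 v 50 | 0.410 | 0.491 | 0.679 | 0.764 |

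Fifty per arm is 25% of 200. Combining 130 per arm with v = 0.418 both charges and credits clustering, so it is a generous end.

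**Step 4: read across.** On 4.4's premise, all-patient power lies between about 0.09 (d = 0.30, single measure, after the design effect) and 0.43 (effect behind N = 90, clustering ignored).

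**The case against.** - **Silence in 8.2 is not exclusion.** The section is short, a fuller list of terms may stand in a statistical analysis plan that is not shown, and tracking signals in every arm suggests a not-on-track analysis was intended. This partly stands: if that analysis is the target, the low figures do not apply to it. But the protocol states both the sized group and the model. A later plan that follows either section departs from the other.
- **Zero effect in on-track patients is only a premise.** Section 1 cites 0.21 overall against 0.31 in flagged patients, and a non-significant effect is not a zero effect. This stands as a sensitivity and could lift power to 0.56 to 0.90 with 200 per arm. Section 4.4, however, does not size on 0.21.
- **The all-patient comparison is the sounder one.** It preserves randomisation and fits the objectives in section 2. This stands, and it is why that model should stay primary.
- **The sample size is not final,** because inclusion may be prolonged after six months. That is true, but dilution to a quarter would need about 1,400 patients before any design effect, using the effect behind N = 90.

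A reader might infer that the primary test will most likely be negative even if feedback works exactly as assumed, with power in some narrow band. The documents do not support that: the assumed effect is not stated, and the power of the actual model over up to 15 sessions cannot be computed without its variance components. A reader might also infer that the not-on-track comparison does have 0.80. At d = 0.30 it does not.

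**Conclusion.** The mismatch is real and needs correcting in the protocol. The 0.80 in section 4.4 refers to a comparison among not-on-track patients, and the test in section 8.2 is made in all patients. Given 4.4's own premise of an effect in 25% and none elsewhere, simple approximations put all-patient power at roughly 0.1 to 0.4, well below 0.80. That range rests on equal allocation, on an effect size that is either d = 0.30 or back-solved from N = 90, and on whether clustering is charged. It is not the power of the random-slope model. The arithmetic from 90 to 554 is correct; the fault lies in which test the resulting power is attached to. The second objective, prediction-model feedback against ROM feedback, is weaker still, because 4.4 expects a difference below d = 0.30 there before any dilution.

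**What to change.** 1. Keep the randomised all-patient model in 8.2 as primary. In 4.4, state the effect size assumed, give the power of that model under the 25% dilution, and say that 0.80 refers only to the not-on-track comparison. Show d = 0.21 as a sensitivity if the sponsor considers it plausible. Use the same target test for the six-month power analysis in 4.4 and 8.3.
2. Prespecify in 8.2 a not-on-track analysis beside it: condition, time and not-on-track status with their interactions, and outcome from the first signal onward. Set status by the same 75% boundary in all three arms, which is already computed because it triggers the ASC in each. Report signal rates per arm, because the Summary lets therapists in both feedback arms view progress at any time, so signalling may itself be affected.

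**Cost.** The changes are to wording and calculation, with no new data. The stated power becomes less favourable. The not-on-track result rests on a group formed after randomisation, and reporting signal rates exposes that problem without removing it. At d = 0.30 with about 50 per arm, the power of that analysis is only about 0.32 to 0.64, or 0.41 to 0.76 with both feedback arms pooled. It should not be described as having 0.80 unless the larger effect behind N = 90 is stated and justified.

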## 6. METHODS

## 6.1 Study parameters/endpoints

## 6.1.1 Main study parameter/endpoint

The main study parameter is the level of the patient's dysfunctioning, measured by the Outcome Questionnaire-45 (OQ-45). Data from session-to-session measurements will be analysed using multilevel modelling. A maximum of 15 sessions was chosen to be analysed. The average amount of sessions is around 9 in the participating centers, but ranges from 1 to more than 100 sessions. If patients are measured until the end of treatment, the longer treatments will have too much influence in the model (because they have more measurement points). As a result, the model is no longer representative for brief treatments. Approximately /4 of treatments are done in 15 sessions, and that is why this number was chosen as a basis for data analysis.

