#### 6.1.3 Other study parameters

Other study parameters include initial severity on the OQ-45 at start of treatment, diagnosis on Axis I and II of the DSM-IV, gender, age and previous treatment for patients. Therapist factors that are studied are: gender, age, years of experience, use of the feedback, therapist expectation of outcome, internal and external feedback propensity and therapist's attitude towards using the feedback.

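### As written, section 8.2 uses the session-1 OQ-45 as both covariate and first outcome, which misstates the patient-level random-effect variances and, in shorter treatments, the standard error of the condition slope

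*Protocol*

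**What the plan says.** Protocol section 8.2 specifies "a three-level random intercept, random slope multilevel model" and states: "The OQ-45 total score is the dependent variable". It then says "Initial severity on the OQ-45 at start of treatment will be included in the model as a covariate", entering it "as a covariate for both the intercept and slope prediction". Condition is coded as two dummy variables. The section does not say whether they act on the intercept, the slope or both.

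The data come from section 6.3 (Procedure): "As from start of treatment, participants will be asked to complete the OQ-45 before each session, for a maximum of 15 sessions". Section 6.1.1 adds: "Data from session-to-session measurements will be analysed using multilevel modelling". Section 6.1.3 lists "initial severity on the OQ-45 at start of treatment" among the other study parameters. No section removes the first session from the outcome.

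**The concern.** Section 6.3 describes no OQ-45 before session 1; intake has the MINI Plus and the SCID-II PQ. Section 9.3 caps the questionnaires at 17, which is 15 sessions plus 2 follow-ups and leaves no room for a separate intake OQ-45. The start-of-treatment score is therefore the session-1 score, and section 8.2 uses it to predict itself.

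This matters because the relation between covariate and outcome differs between session 1 and all later sessions. At session 1 the coefficient is exactly 1 and the residual variance is zero. From session 2 the scores regress towards the mean and have full residual variance. A linear slope with constant residual variance cannot follow that step, so the fit absorbs it in the random effects.

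At stake are the variance components and the standard error that the condition test uses. Section 4.4 also lets observed variance and estimated power decide whether inclusion is prolonged. If that variance were taken from this model, the decision would inherit the distortion.

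**Working it through.** **Plan's own figure.** The protocol states no variance or standard error for the 8.2 model, so there is none to reproduce. Its sample-size chain (90 × 4 = 360; 1 + 3 × 0.18 = 1.54; 1.54 × 360 = 554; target 600) does not depend on this point.

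**Inputs.**
- From the protocol: correlation 0.70 between repeated measures; target of 600 patients in three conditions, taken as 200 each; mean of about 9 sessions, at most 15.
- Assumed: total variance at session 1 of 484, split by 0.70 into intercept variance 339 and residual variance 145 (339/484 = 0.70); slope SD 1 point per session, range 0.5 to 1.5; zero true intercept-slope correlation; linear course; complete data; time counted from session 1.

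**Step 1. What the covariate leaves over.** Let u0 be the patient's random intercept, Y1 the session-1 score and μ its mean. Given Y1:
- E(u0 | Y1) = 0.70 × (Y1 − μ)
- Var(u0 | Y1) = 339 × 145 / 484 = 101.6

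The correct coefficient on the covariate is thus 0.70 from session 2 onward but 1 at session 1. Excluding slope variation, the residual variance is 101.6 + 145 = 246.6 from session 2 onward but 0 at session 1.

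**Step 2. What the 8.2 model converges to.** The working covariance is W = ZGZ′ + σ²I. Its limiting values minimise log|W| + tr(W⁻¹T), where T is the actual residual second-moment matrix, including the misfit of the covariate. The reported squared SE of the condition slope is (2/200) × [(Z′W⁻¹Z)⁻¹]₂₂. The actual one is (2/200) × [(Z′W⁻¹Z)⁻¹ Z′W⁻¹TW⁻¹Z (Z′W⁻¹Z)⁻¹]₂₂.

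Double use, slope SD 1, condition on intercept and slope:

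| Sessions | Intercept variance (correct 101.6) | Intercept-slope correlation (correct 0) | Reported SE | Actual SE | Reported / actual |
|---|---|---|---|---|---|
| 5 | 10.7 | 1.00 | 0.434 | 0.371 | 1.17 |
| 9 | 28.2 | 1.00 | 0.190 | 0.180 | 1.06 |
| 15 | 49.9 | 0.40 | 0.122 | 0.122 | 1.00 |

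Over slope SD 0.5 to 1.5 the intercept variance runs from about 10 to 50. The overstatement of the SE is about 0 to 17% (18% in the single most extreme cell, 5 sessions with slope SD 0.5).

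**Step 3. Slope SE under the alternatives, same assumptions.**

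| Sessions | Session 2 onward, condition on intercept and slope | Session 2 onward, condition on slope only | Constrained longitudinal model |
|---|---|---|---|
| 5 | 0.548 | 0.368 | 0.368 |
| 9 | 0.211 | 0.178 | 0.178 |
| 15 | 0.128 | 0.122 | 0.122 |

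Dropping session 1 while keeping condition on both terms loses precision (0.211 against 0.180 at 9 sessions). The other two alternatives do not.

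**Step 4. Simulation.** REML fits, 600 patients, session-1 variance scaled to 1, correlation 0.70, slope SD 0.03. Double use against session 2 onward:
- Patient intercept variance 0.072 against 0.211. The correct value is 0.70 × 0.30 = 0.21.
- Intercept-slope correlation about +0.95 against about −0.1.
- Slope SE with condition on both terms: 0.0072 against 0.0077, smaller under double use.
- Slope SE with condition on slope only: 0.0070 against 0.0068, larger under double use. The constrained model gives 0.0068.
- Condition on intercept only: estimate −0.030 against −0.108, a loss of 1 − 0.030/0.108 = 72%.

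The slope estimates were not visibly biased (true −0.03, means about −0.029).

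**The case against.** The strongest reply is that the protocol never says in words that the covariate is the session-1 score, nor that the session-1 row stays in the outcome. Which rows enter the model could be settled in an analysis plan that is not shown. That lowers the weight of the point but does not remove it. Section 8.2 fixes both the outcome and the covariate, and the rest of the protocol offers no other OQ-45 at the start of treatment.

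A reader might infer that double use always widens the standard error and costs power. The protocol does not support that. Section 8.2 leaves open where the condition dummies enter, and the direction depends on it. With condition on both intercept and slope, double use usually gives a smaller slope SE than simply dropping session 1. A marked loss of power appears only if the random intercept and slope are forced to be uncorrelated, which section 8.2 does not say.

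A reader might also infer that the question about differences between therapists is compromised. This was not shown. With 50 therapists, 12 patients each, 15 sessions and an assumed therapist slope variance of 0.18, the estimate was 0.181 under double use and 0.176 with session 1 excluded. The effect on therapist variance at the start of treatment was not settled.

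**Conclusion.** The point stands in limited form. Read plainly, section 8.2 uses the session-1 OQ-45 twice. The patient-level intercept variance then comes out far too small (about 10 to 50 instead of about 102) and the intercept-slope correlation spuriously high, up to about 1. The reported SE of the condition slope is overstated by about 0 to 17% in shorter treatments, with little or no effect at 15 complete sessions. With a mean of about 9 sessions, many patients fall in the affected range.

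The slope estimate is not biased under a linear course. It is the intercept-only form of the condition effect that is diluted, by about 70%.

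The sizes rest on assumed variances, since the protocol gives only the correlation of 0.70. The variance distortion itself follows from the double use and appeared throughout the range tried.

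**What to change.** In section 8.2, keep session 1 in the outcome, drop the initial-severity covariate, constrain the three conditions to a common mean at session 1, and let condition act on the slope (a constrained longitudinal model). The common mean is justified because patients are randomised and the first OQ-45 is completed before any feedback can be given. This model uses the same data, and its slope SE was never larger than under double use.

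Alternative: use session 1 only as covariate and sessions 2 to 15 as outcome, with time counted from session 1 and condition on the slope only. Adding condition to the intercept as well would lose precision. In this version, patients with a single session contribute no outcome.

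Either way, state which condition term is the test. The cost is a sentence or two in section 8.2, with no new data and no change to the sample size.

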#### 8.3 Interim analysis

Interim power analysis will be performed after 6 months to test if an appropriate number of patients is included.

## 9. ETHICAL CONSIDERATIONS

#### 9.1 Regulation statement

This study will be performed according to the Ethical Principles of Psychologists and Code Of Conduct by the American Psychological Association (2002).

